9.5 Study Restrictions

Study restrictions and timing of restrictions are summarized in Table 9-1. Subjects may enroll in the study if they are receiving acceptable concomitant medications (according to Table 9-1).

A non-exhaustive list of prohibited medications will be provided in the Study Reference Manual.

[figure not shown]
Table 9-1 Study Restrictions

Restricted Medication/Food/Activity ^a	Timing of Restriction	
	Start	Stop
Other investigational drugs or devices	28 days before screening, 5 half-lives before screening, or time determined by local requirements (whichever is longest)	Completion of the last Safety Follow-up Visit assessments
Augmentation therapy (human alpha-1 proteinase inhibitor)	More than 42 days before antigenic AAT level is obtained for eligibility	Completion of the last Safety Follow-up Visit assessments
UGT1A4/UGT1A1 moderate and strong inhibitors	7 days or 5 half-lives (whichever is longer) before the first dose of study drug	Completion of the last Safety Follow-up Visit assessments
UGT1A4/UGT1A1 moderate and strong inducers	14 days before the first dose of study drug	Completion of the last Safety Follow-up Visit assessments
Tobacco products ^c	6 months before screening	Completion of the last Safety Follow-up Visit assessments

Table 9-1 Study Restrictions

Restricted Medication/Food/Activity ^a	Timing of Restriction	
	Start	Stop
Alcohol: no more than 14 drinks/week for females or 21 drinks/week for males (1 drink = 5 ounces (150 mL) of wine or 12 ounces (360 mL) of beer or 1.5 ounces (45 mL) of hard liquor)	Signing of ICF	Completion of the last Safety Follow-up Visit assessments

^a See Section 9.6 for guidance on concomitant medications.

^c Nicotine replacement therapy under the direction of a physician is allowed.

9.5.1 Exposure to Sunlight

Subjects will take appropriate measures to minimize exposure to ultraviolet radiation (e.g., sunlight, tanning booths) from Day 1 through the last Safety Follow-up Visit.

9.6 Prior and Concomitant Medications

Subjects will follow restrictions described in [Table 9-1](#).

All medications taken from the signing of ICF through the last Safety Follow-up Visit will be recorded with indication, route of administration, and start and stop dates of administration. For subjects who are screened but not subsequently randomized, details of prior medication will only be documented in the subjects' source documents.

Information about bronchodilator use during the study will be recorded for each subject. Use of short-acting and long-acting bronchodilators will be collected and documented in the source documents for each subject.

Information about prior augmentation therapy, as applicable, will be recorded for each subject, including dose, frequency of administration, start and stop dates of last infusion.

9.7 Administration

VX-864 will be administered orally, 2 times a day, approximately 12 hours apart. All subjects will receive the same number of tablets each day to maintain blinding. Additional information is provided in the Pharmacy Manual.

Study drug will be administered according to the following guidelines:

- **Study drug will be taken under the fasted condition.**
The fasted condition is defined as follows: subjects must abstain from all food and drink (except water) for at least 2 hours before and 2 hours after both the morning and the evening dose of study drug on all study days.
- Each subject should take the study drug approximately 12 hours apart (\pm 2 hours). Subjects will swallow the tablet(s) whole without chewing or crushing the tablets with approximately 240 mL of water. Subjects may take additional water (but no food), as needed, to swallow tablets.
- If the subject's scheduled clinic or home visit is to occur in the morning (i.e., before noon), study drug will be administered in the fasted condition after predose assessments have been completed.
- If the subject's scheduled clinic or home visit is to occur in the afternoon, the following guidelines must be followed:
 - o If the dose at the scheduled visit will be within 6 hours of the subject's scheduled morning dose, the subject should withhold the morning dose and the morning dose will be administered in the fasted condition in the clinic or witnessed by a home nurse for home visit.
 - o If the dose at the scheduled visit will be more than 6 hours after the subject's scheduled morning dose, the subject should take the morning dose at home in the fasted condition.
- If the subject's scheduled home visit is to occur in the evening, study drug will be administered after predose assessments have been completed.
- The morning dose of study drug on the Day 28 Visit will be taken in the clinic or at home after the predose PK sample has been drawn. The last dose of study drug will be taken at home in the evening on Day 28, regardless of whether the Day 28 Visit occurs on Day 26 or Day 27.

Missed doses:

If a subject misses a dose, the subject can take the missed dose within 6 hours of the usual dosing time and should take the dose as soon as possible, provided the fasting requirements can be met. If the missed dose cannot be taken under the required fasting condition within 6 hours of the usual dosing time, the subject should skip that dose and resume the normal schedule for the following dose. If more than 6 hours have elapsed after the usual dosing time, the subject should skip that dose and resume the normal schedule for the following dose.

Morning and evening doses should not be taken at the same time.

9.8 Dose Modification for Toxicity

No dose modifications for toxicity are allowed or required. If any unacceptable toxicity arises in the opinion of the investigator individual subjects will discontinue dosing (Section 9.1.4).

9.9 Study Drug Interruption and Stopping Rules

The investigator has the discretion to discontinue study drug treatment at any time if the investigator feels that the subject's continued participation in the study jeopardizes their safety.

Any subject with worsening of AATD or disease progression that, in the judgement of the treating physician, requires (re)initiation of standard of care treatment (per local guidelines) that is prohibited in this study (including augmentation therapy) will discontinue study drug treatment.

Any subject with QTcF values above the threshold values as described in Section 11.5.4 will discontinue study drug treatment.

Study drug treatment may be interrupted for safety concerns at discretion of the investigator.

Study drug administration must be interrupted immediately (before confirmatory testing), and the medical monitor must be notified, if any of the following criteria are met:

- ALT or AST $>5 \times$ ULN
- Total bilirubin $>3 \times$ ULN
- ALT or AST $>3 \times$ ULN associated with total bilirubin $>2 \times$ ULN and/or clinical jaundice

Subjects with new treatment-emergent ALT or AST elevations of $>3 \times$ ULN, or total bilirubin $>2 \times$ ULN, must be followed closely, including confirmatory testing performed within 48 to 72 hours of the initial finding and there must be close monitoring of ALT, AST, and bilirubin levels thereafter, as clinically indicated.

If a subject cannot return to the site for confirmatory testing, a local laboratory may be used. Local laboratory results must be reported immediately to the medical monitor, and the subject must have the tests repeated and sent to the central laboratory as soon as possible (ideally within 48 to 72 hours).

In subjects who met above interruption criteria, a thorough investigation of potential causes should be conducted, and the subject must be followed closely for clinical progression. If an alternative, reversible cause of transaminase elevation and/or increased bilirubin has been identified, study drug administration may be resumed once transaminases and/or bilirubin return to baseline or are $<$ ULN, whichever is higher. **Approval of the medical monitor is required before resumption of study drug.** Upon resumption of study drug, transaminases and bilirubin must be assessed weekly until 7 days after the last dose of study drug. If a protocol-defined transaminase and/or bilirubin elevation interruption threshold recurs, then study drugs must be permanently discontinued, regardless of the presumed etiology.

All subjects for whom treatment is discontinued for elevated transaminases and/or bilirubin should have these levels monitored closely until levels normalize or return to baseline.

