Spirometry	X	Spirometry will be performed post-bronchodilator and according to the American Thoracic Society Guidelines/European Respiratory Society Guidelines. If spirometry cannot be performed, historical post-bronchodilator ppFEV ₁ results measured within 1 year before screening can be used to determine eligibility. Section 8.2 exclusion criterion #7 and Section 11.5.5 .
Urine cotinine	X	Section 11.5.2
AEs and SAEs	Continuous from signing of ICF through last Safety Follow-up Visit	Section 11.5.1
Medications review	Continuous from signing of ICF through last Safety Follow-up Visit	Section 9.6

AAT: alpha-1 antitrypsin; Ab: antibody; AE: adverse event; β -hCG: beta-human chorionic gonadotropin;

FSH: follicle-stimulating hormone; HBsAg: hepatitis B surface antigen; HCV: hepatitis C virus;

HIV-1/HIV-2 Abs: antibodies against human immunodeficiency viruses 1 and 2; ICF: informed consent form;

ppFEV₁: percent predicted forced expiratory volume in 1 second; SAE: serious adverse event

Note: Screening procedures (including informed consent) can be performed over more than 1 day. Informed consent must be obtained prior to any procedures. Repeat Screening assessments and Screening assessments that were not conducted at the initial visit during the Screening Period may be performed at the clinic or at home by a qualified visiting nurse, if permitted by ethical and regulatory authorities and agreed upon after investigator and subject consultation.

Table 3-2 Study VX19-864-101: Screening for Subjects Who Have Been on Augmentation Therapy at Any Time

Event/Assessment	Screening Period Day -70 through Day -1	Comments
Informed consent	X	Section 13.2.3
Inclusion and exclusion criteria review	X	Sections 8.1 and 8.2
Clinic visit	X	
Demographics	X	
Medical history	X	Section 11.1
Medications review	X	Section 9.6
Prior augmentation therapy review	X	Subjects must discontinue augmentation therapy >42 days before the antigenic AAT levels are obtained to determine eligibility. Subjects can resume augmentation therapy after completion of the Safety Follow-up Assessments. Section 9.6

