8.1 Inclusion Criteria

1. Subject will sign and date an informed consent form (ICF).
2. Willing and able to comply with scheduled visits, treatment plan, study restrictions, laboratory tests, contraceptive guidelines, and other study procedures.
3. Subjects will be 18 through 80 years of age, inclusive, at the time of signing of the ICF.
4. All female subjects must have a negative pregnancy test at screening (serum test). Premenopausal female subjects of child-bearing potential must also have a negative pregnancy test on Day 1 (urine test) and must not be breastfeeding or planning to become pregnant during the study or within 90 days after the last study drug dose.
5. Body mass index (BMI) of 18.0 to 35.0 kg/m², inclusive.
6. Subjects must have a *PiZZ* genotype confirmed at screening.

NOTE: *PiZZ* genotype must be tested at the central laboratory. Historical genotype results can be used to determine eligibility if they were obtained as part of a different Vertex study. In addition, if the screening *PiZZ* genotype result is not received before randomization, a previous non-Vertex *PiZZ* genotype laboratory report (approved by the medical monitor or designee) may be used to establish provisional eligibility. **Subjects who have been randomized and whose screening genotype subsequently does not confirm study eligibility must be discontinued from the study (Section 9.10).**

7. Plasma antigenic AAT level <8 µM during screening.

NOTE: For subjects who have been on augmentation therapy at any time, results used to confirm eligibility must be drawn >42 days after the last dose of augmentation therapy. Antigenic AAT levels must be obtained from the central laboratory and results confirmed before randomization.

8. Willing to remain off of augmentation therapy from >42 days before antigenic AAT levels are obtained for eligibility through the last Safety Follow-Up Visit.

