Notes: Figure is not drawn to scale. Subject numbers include subjects who have never been on augmentation therapy and subjects who have been on augmentation therapy at any time. Subjects must discontinue augmentation therapy >42 days before antigenic AAT levels are drawn and sent to the central laboratory to confirm eligibility; results must be confirmed to be <8 μM before randomization. Once antigenic AAT levels have been confirmed to meet this eligibility criterion, randomization and Day 1 can occur any time within the remaining screening window. Sites should allow at least 14 days for sample processing and antigenic AAT level results reporting. Subjects can resume augmentation therapy after completion of assessments at the last Safety Follow-up Visit.

*Blood samples will be obtained for antigenic and functional AAT levels at the same time that the other screening laboratory assessments are performed. If the subject received the last dose of augmentation therapy >42 days prior, this sample can be used to measure antigenic AAT level for eligibility. If samples are obtained ≤42 days after the last dose of augmentation therapy, another sample must be drawn >42 days after the last dose of augmentation therapy and sent to the central laboratory to confirm eligibility.

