9.1.1 Screening

For subjects who have never been on augmentation therapy, the Screening Period (Day -35 through Day -1) will occur up to 35 days before the first dose of study drug.

For subjects who have been on augmentation therapy at any time, the Screening Period (Day -70 through Day -1) will occur up to 70 days before the first dose of study drug. The last dose of augmentation therapy must have been given >42 days before the antigenic AAT levels are obtained to confirm eligibility. To establish eligibility, an antigenic AAT level must be drawn >42 days after the last dose of augmentation therapy and sent to the central laboratory. The antigenic AAT result must be reviewed to confirm eligibility before randomization. Subjects will remain off augmentation therapy thereafter until after the last Safety Follow-up Visit has been conducted.

Screening assessments will be used to confirm that subjects meet the eligibility criteria. The investigator (or an appropriate authorized designee at the study site) will obtain informed consent from each subject before any study procedure takes place. Screening procedures (including informed consent) can be performed over more than 1 day. Informed consent must be obtained prior to any procedures. Screening assessments that were not conducted at the initial visit during the Screening Period may be performed at home by a qualified visiting nurse or at the clinic (if permitted by ethical and regulatory authorities and agreed upon after investigator and subject consultation).

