9.1.2 Treatment Period

The Treatment Period will be randomized, double-blind, and placebo-controlled. It will last approximately 28 days. Study drug administration details are provided in [Section 9.7](#).

Subjects who prematurely discontinue study drug treatment will remain in the study from the time of discontinuation of study drug treatment through the last scheduled study visit and complete assessments for all study visits, as described in [Section 9.1.4](#).

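### Section 9.9 stops study drug when augmentation is required, but Section 9.1.1 and Table 9-1 keep augmentation barred until the last Safety Follow-up Visit, with no exception for that subject

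*Protocol*

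**What the plan says.** **The stopping rule.** Protocol Section 9.9 covers worsening AATD or disease progression that, as the treating physician judges it, "requires (re)initiation of standard of care treatment (per local guidelines) that is prohibited in this study (including augmentation therapy) will discontinue study drug treatment". Stopping study drug is the only action it sets. It does not say whether or when the required treatment may begin.

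**The subject stays in the study.** Section 9.1.2: "Subjects who prematurely discontinue study drug treatment will remain in the study from the time of discontinuation". Section 9.1.4 requires both Safety Follow-up Visits after an early stop, and Section 9.10 continues follow-up unless consent is withdrawn.

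**Direct restrictions on conduct.**
- Section 9.1.1: "Subjects will remain off augmentation therapy thereafter until after the last Safety Follow-up Visit has been conducted".
- Section 9.5, Table 9-1, augmentation row: starts "More than 42 days before antigenic AAT level is obtained for eligibility"; stops at "Completion of the last Safety Follow-up Visit assessments".

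**Passages that echo the restriction.**
- Notes to Protocol Figures 2-2 and 9-2 and to SAP Figure 7-2: "Subjects can resume augmentation therapy after completion of assessments at the last Safety Follow-up Visit".
- Protocol Table 3-2: "Subjects can resume augmentation therapy after completion of the Safety Follow-up Assessments".
- Inclusion criterion 8 (Section 8.1): "Willing to remain off of augmentation therapy from >42 days before antigenic AAT levels are obtained for eligibility through the last Safety Follow-Up Visit".

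**The concern.** Section 9.9 foresees a subject for whom augmentation has become necessary and takes that subject off study drug for this reason. The restriction that makes augmentation unavailable is tied to a visit about four weeks later, and nothing visible lifts it for this subject. A site that reads Section 9.9 alone would probably start treatment. A site that reads Table 9-1 alone would conclude that treatment is still prohibited.

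Two things are at stake. Read literally, the text delays treatment that the protocol's own rule describes as required. Sites may also act differently in the same situation, and those that treat must record a deviation. The situation is tied to the design, because previously augmented subjects have to be off therapy for more than 42 days before the eligibility sample.

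**Working it through.** This is mainly a comparison of passages, with simple addition for the length of the restriction.

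**1. The plan's own duration.** The synopsis gives 28 treatment days and 28 follow-up days: 28 + 28 = 56 days, which matches its stated approximate total. The last Safety Follow-up Visit is therefore nominally 28 days after the last dose.

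**2. Length of the restriction after an early stop.** Table 3-3, footnote e, places the last Safety Follow-up Visit 28 (±2) days after the last dose for subjects who stop early.
- Earliest: 28 − 2 = 26 days.
- Latest: 28 + 2 = 30 days.
- Under Section 9.1.4, an ETT Visit 22 or more days after the last dose replaces that visit, so the restriction could then end from 22 days.

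These intervals run from the last dose, not from the decision to stop.

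**3. How strongly each passage restricts.**
- Direct bar on conduct: Section 9.1.1 and Table 9-1 (2).
- Statement of when augmentation can resume: notes to Figures 2-2 and 9-2, Table 3-2, and the note to SAP Figure 7-2 (4).
- Willingness at entry: inclusion criterion 8 (1).

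The total is 2 + 4 + 1 = 7 places, six in the protocol and one in the SAP. The conflict rests on the first two; the others repeat it. Section 9.1.2 contains no augmentation bar; it matters only because it keeps the subject in the study.

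**4. Who is covered.** The Section 9.1.1 sentence belongs to the paragraph on subjects who have been on augmentation at any time. The Table 9-1 row is not limited in that way. Section 9.9 covers both starting and restarting, so for a subject never augmented before, Table 9-1 is the direct bar.

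**5. Is there an exception?** None is visible in Sections 9.1.1, 9.1.4, 9.5, 9.9 or 9.10 for a subject who stops under this rule.

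**6. What a site can do under the text.** Section 13.1.1.1 counts worsening of a pre-existing condition as an AE. Section 13.1.1.8 makes the investigator responsible for adequate care of AEs. Section 13.2.4 provides for immediate departures from the protocol, with sponsor contact and an entry in the deviation log. Treatment with continued follow-up is therefore possible, but as a deviation.

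**7. Effect on data.** Table 3-3 schedules functional and antigenic AAT samples at the ETT and Safety Follow-up Visits. SAP Section 9.1 limits the use of AAT values after augmentation only when defining baseline. Its optional exclusion analysis covers values influenced by PEx or COVID-19 vaccination and does not name augmentation. The visible text does not say how post-baseline AAT values after augmentation are handled; redacted text may.

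**The case against.** The best defence is that Section 9.9 is the specific rule. It acknowledges the prohibition, names augmentation, and makes stopping study drug the consequence, so the natural reading is that drug stops in order that treatment can start. The resumption notes describe the scheduled path, and criterion 8 is a test at entry. Exclusion criteria 9 (unstable AATD-related COPD) and 22 (stopping augmentation not in the subject's best interest) make the case less likely. Visible Table 9-1 footnotes run from a to c, so part of the table may not be visible.

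Much of this stands. The problem is a missing exception, not two opposite explicit orders, and few subjects should be affected. But an implied permission does not override two unqualified restrictions, one of them in the table that Section 9.6 tells subjects to follow. The visible augmentation row carries no marker for the absent footnote, so that gap lowers confidence slightly and settles nothing.

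A reader might infer that the only way to receive treatment is to withdraw consent and lose follow-up. The documents do not support this: Sections 13.1.1.8 and 13.2.4 allow treatment as a documented departure while follow-up continues. A reader might also add washout, result turnaround and treatment days into one long period without augmentation. Most of that time is planned by the design and precedes the conflict. Only the interval after the last dose is in question.

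**Conclusion.** The concern holds as an unreconciled conflict between Section 9.9 on one side and Section 9.1.1 and Table 9-1 on the other. For a subject stopped under this rule, the written restriction continues for 26 to 30 days after the last dose, or from 22 days with a late ETT Visit. Care is not made impossible, but giving it counts as a protocol deviation in a situation the protocol anticipates.

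The documents give no rate for this event. That it is rare is a judgement based on the short treatment period and the exclusion criteria. The conclusion assumes that no redacted text supplies the exception. It takes no position on which clinical rule should apply. It is worth correcting because it bears on subject safety and consistent site conduct; it does not call the primary analysis into question.

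**What to change.** Reconcile Section 9.9 with the augmentation row of Table 9-1 and with Section 9.1.1, so that all three give one instruction on when the restriction ends for a subject stopped under this rule. A cross-reference can cover the notes to Figures 2-2 and 9-2, Table 3-2 and the note to SAP Figure 7-2, so these need no separate rewriting. Sections 9.1.4 and 9.10 already require follow-up after an early stop. The sponsor and its clinicians decide which rule holds.

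The cost is wording in one amendment. The downside is that, if treatment is allowed earlier, later AAT samples from that subject may be affected by augmentation. Section 9.6 already requires medication start dates to be recorded, so such samples can be identified. In that case one sentence in the SAP, unless redacted text already has it, should say how they are handled.
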